
2.2 Background & Rationale, Significance of Selected Topic & Preliminary Data
	
Nexplanon, an etonogestrel implant, is a safe, highly-effective and well-tolerated method of long-term birth control. In fact, implants are in the top tier of effective contraception (1). Providing women who have had a second trimester termination with the option of an implant could significantly reduce unplanned and undesired future pregnancies. Immediate rather than delayed implant insertion after a termination of pregnancy may be beneficial for several reasons. The most compelling argument is poor post-operative follow up rates. On a national level the percentage of patients that do not return for this visit is about 35-60% (2). Given the poor follow-up rate, failure to utilize the immediate post procedure period to provide patients with effective long-term contraception is likely to lead to a subsequent undesired pregnancy. Additional benefits of post-procedure insertion include greater patient motivation for contraceptive use as well as avoidance of additional discomfort from a second procedure at a later date (4). A recent study by the primary investigator, [name], showed that women randomized to immediate insertion were significantly more likely to have an IUD at 6 months compared to delayed (81.7% vs. 28.4%, p=.003). Relative risk was 11.2 (95% CI 5-26) (5). A similar, observational study by Tocce, et al. showed similar results to immediate vs. delayed placement of post-partum etonogestrel implant among adolescents (6). There are no studies to date in a post-abortion population and this information would help guide management.

2.3 Study Design
	
This is a randomized controlled trial comparing immediate vs. delayed placement of Nexplanon after second trimester abortion procedures. Enrollment will be conducted at Family Planning Associates Medical Group (FPA) in Chicago. This is an independent medical group that is the leading abortion provider in the Chicago area, providing over 1,800 second-trimester abortions per year.
 
[name] successfully conducted a similar study at Parkmed and Bellevue Hospital on immediate vs. delayed IUD placement after second trimester abortion (5).
 
[name], the physician in charge of the study at FPA, is a board certified Obstetrician Gynecologist who completed a Family Planning fellowship, an ACOG member, and the former Director of the Fellowship in Family Planning at the University of Illinois at Chicago.

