- Pregnancy, reproductive, contraceptive, general health histories
- Height and weight
- Results of general appearance exam and other body systems (if indicated)
- Concomitant medications
- Documentation of contraceptive counseling

All participants will undergo termination of pregnancy by dilation and evacuation (D&E) at Family Planning Associates. Eligible participants will complete enrollment before placement of dilators, which is usually performed one day prior to the D&E, but may be the same day, per clinic protocol. Participants will be randomized after the D&E procedure is complete to either "immediate" or "delayed" Nexplanon placement. Insertion of dilators will be performed by either first-clinician [name], P.A., or [name]. All D&Es, as well as all Nexplanon insertions, will be performed by [name]

[name] at FPA. She is trained and approved to place Nexplanon and will place all devices in women enrolled at FPA.

Since randomization occurs after the abortion, both groups will undergo a termination of pregnancy in the exact same manner. Participants in the immediate group will have an etonogestrel rod placed within 15 minutes following the procedure, and while still anesthetized. Participants in the “delayed” placement group will be asked to return to FPA for a post-abortion visit 2-4 weeks following the procedure. Participants in the delayed group will be offered a method of contraception to use in the interim between their procedure and their insertion appointment. At their follow-up visit, an etonogestrel rod will be placed in their arm using standard procedure.

Women randomized to “delayed” insertion will receive one reminder phone call, email, or text message (method of their choosing) about their appointment from the research staff. Attempts will not be made to contact them after a missed appointment.

In the event that participants miss their appointment for Nexplanon placement and still desire the device, they are eligible for placement up to 6 months after their abortion procedure. Under this circumstance, it is the subject’s responsibility to coordinate an appointment with the research office.

All participants will receive a phone call from a research assistant at 6 months to complete a Satisfaction Questionnaire.

Delayed Insertion Visit

The following procedures will be conducted at the delayed insertion visit.

- Review of contact information/emergency contact information

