- Review of concomitant medications and contraception since D&E procedure
- Review of adverse events since D&E
- Confirmed continued eligibility to receive Nexplanon
- Review of sexual intercourse history since D&E procedure
- Staff-administered Delayed Insertion Questionnaire
- Collection of vital signs (blood pressure, pulse)
- Directed physical exam
- Insertion of Nexplanon device using standard procedure

Additional procedures to be performed if visit is conducted outside of 2-4 week window

- Urine pregnancy test
- Review of sexual intercourse since LMP

Phone Call (6 month) Procedures

Participants will be contacted by research staff 6 months (+/- 2 weeks) after

	
their abortion procedure. A Satisfaction Questionnaire will be completed during the phone call. Participants will be asked to palpate their implant while on the phone to confirm current use of Nexplanon. Phone calls completed out of window will be documented as a protocol deviation. Those who complete this follow-up will have their addresses re-confirmed and a \$25 gift card will be mailed to them.
 
Comparison Groups and Outcomes Participants who are randomized to have Nexplanon placed immediately post procedure will be compared to participants who were randomized to have Nexplanon placed 2-4 weeks post procedure. The primary outcome will be participants using Nexplanon at 6 months following the procedure. Secondary outcomes will be repeat pregnancy rates, side effects, and contraceptive method satisfaction as assessed by the Satisfaction Questionnaire. Data will also be collected on women who return to have their Nexplanon placed beyond the 2-4 week post-procedure period. Within- and between-group analyses will also be performed to see if insurance status or history of RC/IPV are predictors of the primary or secondary outcomes.

2.6 Study Duration
	
24 months

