
2.7 Statistical Analysis and Sample Size Justification
	
The data will be analyzed by a contract statistician, [name] at the University of Southern California.
 
STATISTICAL METHODS: The primary outcome to be analyzed is the percentage of women using Nexplanon at the end of 6 months. This analysis will be done with a chi-square test. Secondary outcomes to be analyzed include the proportion of participants using other high or middle tier contraception, pregnancy rates, side effects and satisfaction with the procedure.
 
SAMPLE SIZE: We aim to recruit 120 women seeking termination over 2 years who agree to participate in this study and desire to have Nexplanon as their postpartum contraceptive method. The sample size was calculated based on a power of 0.80 to demonstrate a 20% difference in usage rates of Nexplanon between groups, assuming 40% of women overall are not using Nexplanon six months after their procedure.
 
RANDOMIZATION/SEQUENCE GENERATION/IMPLEMENTATION Prior to randomization allocation of treatment will be unknown by the investigators or the patient. Consent will be obtained prior to the scheduled procedure. However, randomization will occur immediately after the procedure in the operating room, while the patient is still sedated. Sequentially numbered, opaque, sealed envelopes will be placed in the FPA office. An unopened envelope will be placed in the participant’s chart before

the procedure. If the subject changes her mind about participation, the envelope will be returned unopened to the FPA office. Participants will be randomized using a computer-generated table of random numbers. A permuted block design will be used, with a block size of 10. However, since two subjects were recruited at another site that was closed for the study before the completion of follow-up, the first block will be a block of 8.

Blinding:

After randomization, neither the participants nor the physicians will be blinded to the treatment.

Withdrawals, Losses and Deviations:

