Every attempt will be made to minimize withdrawal from the study. In the event that a woman does withdraw from the study, the investigators will try to determine the reason for the withdrawal and include this information in the analysis. Participants will be contacted 6 months following the procedure and asked to complete a Satisfaction Questionnaire. Participants will be asked to palpate their device while on the phone. If the device is palpable she will be considered as using Nexplanon at 6 months. In the rare case that the participant cannot palpate the device she will be brought in to FPA for clinician evaluation (unscheduled visit).

Research staff will make at least three attempts to contact participants by phone at 6 months. If these attempts are unsuccessful a certified letter and U.S. mail letter will be sent to the participant's last known address. If the certified letter is returned to the research office unopened, staff will contact the participant's emergency contact provided at enrollment.

This patient population is at high-risk for loss to follow-up. At enrollment participants will give their contact information as well as names and phone numbers of two people who do not live with them who may be able to contact them in case they cannot be reached. To ensure that we reach the 120 sample size we will enroll 150 women since there will be a proportion of women who cannot be reached at the end of the study.

All participants will be compensated \$75 for participation at screening/enrollment. Participants in the delayed group will receive \$15 at their follow-up visit for Nexplanon placement. Finally, all participants will be compensated with a \$25 gift card, delivered by mail, after completing the Satisfaction Questionnaire at 6 months.

Patients who deviate from the protocol will be analyzed according to their allocation group at the time of enrollment (intention-to-treat).

Data Collection/Outcome Measurement

All patients undergoing termination of pregnancy will have a complete history, physical exam and routine labs prior to the procedure. This

	
information will be filled out on a data extraction form following enrollment. Subjects who are enrolled in the study to delayed placement will have an extra visit to place the device. All subjects will be contacted by phone at 6 months to fill out a questionnaire and a satisfaction survey.

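### Does the 24-month study duration in section 2.6 cut off the 6-month endpoint for women recruited late in a 2-year accrual period?

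*Combined protocol and SAP*

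**What the plan says.** Section 2.6 (Study Duration) contains one entry, 24 months, with no breakdown into accrual and follow-up.

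Section 2.7, under Sample Size, states: "We aim to recruit 120 women seeking termination over 2 years". Under Withdrawals, Losses and Deviations it adds: "To ensure that we reach the 120 sample size we will enroll 150 women", to allow for women who cannot be reached at the end.

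The endpoint is defined in section 2.5: "The primary outcome will be participants using Nexplanon at 6 months following the procedure". The same section gives the timing, counted from the abortion: "Participants will be contacted by research staff 6 months (+/- 2 weeks) after". It also says who is covered: "All participants will receive a phone call from a research assistant at 6 months to complete a Satisfaction Questionnaire". Section 2.7, under Data Collection/Outcome Measurement, repeats this: "All subjects will be contacted by phone at 6 months".

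The clock starts almost at enrollment. Section 2.5 places enrollment before dilator placement, usually the day before the procedure or the same day. Section 2.7 says that "randomization will occur immediately after the procedure in the operating room, while the patient is still sedated".

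**The concern.** Taken at face value, three statements cannot all hold: a 24-month study, 2 years of recruitment, and a 6-month endpoint for every woman. Recruitment alone uses up the whole stated duration.

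The risk would lie in applying section 2.6 literally. If data collection stopped at month 24, women recruited in the last 6 months would have no primary outcome. The increase from 120 to 150 would not cover that loss, because it is justified only by women who cannot be reached.

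A second, smaller uncertainty is which number the 2 years belongs to: the 120 in the sample size paragraph or the 150 to be enrolled.

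**Working it through.** **Inputs.** Duration 24 months (2.6). Recruitment 2 years = 24 months (2.7). Endpoint at 6 months, window 2 weeks either side (2.5), i.e. 14/30.4375 = 0.46 month. Enrollment 150 for 120 reached (2.7). Site volume "providing over 1,800 second-trimester abortions per year" (2.3).

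**1. Can the 24 months be reproduced?**
- As accrual only: 2 years = 24 months. It matches.
- As accrual plus follow-up: 24 + 6 = 30 months. It does not match.
- As a total that includes follow-up: accrual would have to end by 24 − 6 = 18 months, or 24 − 6.46 = 17.5 months if the late edge of the window is kept. That contradicts the 2 years.

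The figure fits only as the accrual period.

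**2. Date of the last endpoint.** The target is 24 + 6 = month 30.0. The window opens at 30 − 0.46 = 29.5 and closes at 30 + 0.46 = 30.5. The stated duration is thus short by 5.5 to 6.5 months. The letters and emergency-contact tracing in section 2.7 come on top; the plan gives no time for them.

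**3. Does anything use the duration?**
- The sample size in 2.7 rests on power 0.80, a 20-point difference and 40% overall non-use. Calendar time does not enter.
- The primary analysis is a chi-square test of the proportion using the device at 6 months. It depends on each woman's own time since her procedure.
- Section 2.5 and section 2.7 both require the call for everyone. Section 2.7 adds at least three call attempts, then letters, then emergency contacts.
- No section sets a common closing date.

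**4. What a literal closure at month 24 would cost.** Assume 150 women accrued uniformly over 24 months. Then 6/24 = 25% (37.5 women) would have no endpoint, leaving 112.5. At the implied reach of 120/150 = 80%, 112.5 × 0.8 = 90 women are evaluable, or 45 per arm.

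Take 70% against 50% use (40% overall non-use and a 20-point difference) and two-sided 0.05, which the documents do not state. With z the standard normal variable, power = P(z < [0.20 − 1.96·√(0.48/n)] / √(0.46/n)):
- n = 60 per arm: (0.20 − 0.1753)/0.0876 = 0.28, power 0.611.
- n = 45 per arm: (0.20 − 0.2024)/0.1011 = −0.02, power 0.490.

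The share lost depends heavily on the accrual shape: (6/24)² = 6% if accrual declines linearly to zero, 1 − (18/24)² = 44% if it rises linearly from zero. The gap between 0.611 and the stated 0.80 is a separate sample size matter and has nothing to do with the duration.

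**5. Could accrual end early instead?** Enrolling 150 in 24 months needs 150/24 = 6.25 women per month; in 17.5 to 18 months it needs 8.6 to 8.3. Against 1,800/12 = 150 procedures per month, that is 4.2% compared with 5.7% to 5.6%. The documents give no eligibility or consent rate, so they cannot show whether the faster rate is attainable.

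**The case for a change.** The strongest argument for a change is that the end of the study has practical consequences. Section 2.8 returns unused devices to the manufacturer at that point. Section 2.5 lets women in the delayed group who miss their appointment receive the device up to 6 months after the procedure, and says the clinic offers it only through the study. A literal end at month 24 would shorten that opportunity for late recruits in one arm only, and so would bear on the primary comparison. Section 2.7 also records a site that closed before follow-up was complete, so early closure has happened. Finally, section 2.12 names a date for manuscript submission, and correcting section 2.6 would take a few words.

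The inconsistency itself stands, and 30.5 months is a minimum because tracing takes further time. The consequences do not stand. Each needs the study to end at month 24, and the plan's instruction to call every woman at 6 months excludes that. The closed site was an event that affected two women, which the randomization text handles with a first block of 8; it is not a rule for stopping follow-up. The submission date cannot be tested against the timeline, because the documents give no start date.

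The question of 120 or 150 is largely answered by section 2.7: 150 are enrolled so that about 120 are reached. Section 2.8 requests 150 devices, which agrees. Holding accrual at 120/24 = 5 per month and stretching it to 150/5 = 30 months is arithmetically possible, but no section plans it.

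**Conclusion.** The figures in sections 2.6 and 2.7 do not add up. Read as total duration, 24 months falls about 6 months short of the last endpoint call (5.5 to 6.5 months across the call window). The most plausible reading is a clerical slip in which section 2.6 repeats the accrual period.

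No change to the plan follows. A team that carries out sections 2.5 and 2.7 as written calls every woman 6 months after her own procedure, obtains the same data, runs the same test and reaches the same conclusion, whatever section 2.6 says. The 25% loss of endpoints and the fall in power from 0.611 to 0.490 describe a closure that the plan does not contain; they also rest on an assumed accrual shape, 20% loss and an assumed two-sided 0.05. Ending accrual at about month 18 to keep a 24-month total would be a trade-off of feasibility that the documents cannot settle.

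This conclusion assumes that follow-up runs to the last woman's call. It would change only if the sponsor meant month 24 as a firm end of data collection, and nothing in the text says so.

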2.1 Objectives & Hypotheses

2.1 List the objectives.

The primary aim of this study is to determine if Nexplanon placed immediately after termination of a second trimester pregnancy vs. 2-4 weeks post-procedure improves use of Nexplanon at 6 months following the pregnancy termination. Secondary objectives include determining the rates of satisfaction, side effects, and repeat pregnancies in each group.

Exploratory objectives:

- To examine the type of insurance plan that women seeking a second trimester surgical abortion, who also desire Nexplanon for contraception, are enrolled in. Additionally we seek to determine if insurance status is a covariate of the primary endpoint.
- To measure the prevalence of lifetime and recent reproductive coercion (RC) and intimate partner violence (IPV) in women seeking second trimester surgical abortion, who also desire Nexplanon for contraception.

2.1.1 List the clinical hypotheses.

- Women who receive Nexplanon immediately post abortion will be significantly more likely to be using the device 6 months after the procedure than those assigned to receive the device 2-4 weeks after the procedure.
- Women in the immediate insertion group will report significantly greater satisfaction, the same or fewer side effects, and fewer repeat pregnancies than those in the control group.
- Women with private health insurance will be significantly more likely to be using the device 6 months after the procedure than those who have public health insurance or no insurance at all.
- Insurance status is a significant covariate in predicting the primary endpoint.
- Women with a history of RC/IPV at the time of enrollment will have greater odds of having a prior abortion compared with women who report no history of RC/IPV.
- Among women randomized to the delayed insertion group, those with a history of RC/IPV at the time of enrollment will be less likely than those without a history of RC/IPV to return to the clinic 2-4 weeks later for Nexplanon insertion.

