
2.8 Specific Drug Supply Requirements
	
We are requesting 150 Nexplanon devices to use for the study. All devices will be accounted for and any unused devices will be shipped back to Merck at the end of the study.

2.9 Adverse Experience Reporting
	
Adverse Event (AE)
 
An adverse event (AE) is any untoward or undesirable event experienced by a participant regardless of whether the event is expected or related to the participant’s involvement in the research. Possible adverse events unique to this study include complications from Nexplanon insertion.
 
Serious Adverse Event (SAE)
 
A serious adverse event (SAE) is any untoward medical occurrence or effect involving
 
 ▪ Death ▪ A life-threatening condition (participant at immediate risk of death) ▪ Persistent or significant disability/incapacity ▪ In-patient hospitalization or prolongation of existing hospitalization ▪ A congenital anomaly or birth defect ▪ An important medical event that may jeopardize the participant or may require intervention to prevent one of the outcomes listed above. 
Unanticipated Problems
 
In addition to adverse events as described above, there are events that occur during studies that represent unanticipated problems but are not considered adverse events. In other words, harm to a participant need not occur in order for an event to be an unanticipated problem e.g., laptop with data is stolen.
 
Procedures
 
The Site Investigator, [name], will report AEs, SAEs, and unanticipated problems to the Principal Investigator, [name], to be reviewed and evaluated throughout the study. [name] will decide how to report these according to the guidelines below.
 
All SAEs will be followed until satisfactory resolution or until the PI deems

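### Section 2.7 claims 0.80 power with 120 women for a 20-point difference; at a two-sided 5% level with equal arms (70% vs 50% use), power is about 61%

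*Combined protocol and SAP*

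**What the plan says.** The sample size paragraph of section 2.7 sets the target: "We aim to recruit 120 women seeking termination over 2 years". Its basis is one sentence: "The sample size was calculated based on a power of 0.80 to demonstrate a 20% difference in usage rates of Nexplanon between groups". The only event rate behind that calculation is a single figure for non-use, not split by arm: "assuming 40% of women overall are not using Nexplanon six months after their procedure". For the primary outcome, Nexplanon use at 6 months, section 2.7 says: "This analysis will be done with a chi-square test".

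On allocation it says only: "A permuted block design will be used, with a block size of 10". No ratio is given, and neither a significance level nor the sidedness of the test appears anywhere in the document.

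The part of section 2.7 on withdrawals and losses makes 120 the number left after losses: "To ensure that we reach the 120 sample size we will enroll 150 women". Section 2.8 agrees with a study total of that order: "We are requesting 150 Nexplanon devices to use for the study". So 120 is the total with 6-month data, not a per-arm figure.

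**The concern.** A 20-point difference between two proportions near 60% usually needs well over 60 women per arm for 80% power, so 120 in total looked too few. The sentence is the only justification of the sample size, and it concerns the primary endpoint. If it is wrong, the trial has a much larger chance of missing the difference it was planned to find. A reader of a null result who relied on 0.80 would also overstate the evidence against a 20-point difference.

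**Working it through.** **Inputs from section 2.7:** power 0.80; 20% difference, read as 20 percentage points; 40% overall non-use, so 60% overall use; chi-square test; 120 evaluable women.

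**Assumed, because the plan is silent:** 5% level, two-sided (an ordinary chi-square test is two-sided), 1:1 allocation, hence n = 60 per arm.

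**Arm rates.** With equal arms, mean use of 60% and a gap of 20 points give p1 = 0.70 (immediate) and p2 = 0.50 (delayed).

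**Trying to reproduce the plan's figure.** Pooled-variance formula, with m the mean of p1 and p2:

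Power = Φ{ [ |p1 − p2|·√n − z·√(2m(1 − m)) ] / √( p1(1 − p1) + p2(1 − p2) ) }

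- |p1 − p2|·√n = 0.20 × √60 = 1.549
- z·√(2m(1 − m)) = 1.960 × √0.48 = 1.358
- √(0.21 + 0.25) = √0.46 = 0.678
- Power = Φ(0.191 / 0.678) = Φ(0.282) = **0.611**

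Enumerating the binomial outcomes for the Pearson chi-square test without continuity correction gives 0.618; with Yates correction, 0.542. The stated 0.80 is not reproduced.

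**Number needed for 0.80:** n = (1.960 × √0.48 + 0.842 × √0.46)² / 0.20² = (1.358 + 0.571)² / 0.04 = 93 per arm, or 186 evaluable. The plan's loss allowance is 1 − 120/150 = 20%, so this means 186 / 0.80 = 232.5, i.e. 233 enrolled.

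**Other readings, 60 per arm, 5% level, same formula:**

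| Use, immediate vs delayed | Reading of the 40% non-use | Two-sided | One-sided |
|---|---|---|---|
| 70% vs 50% | both arms together, as written | 0.611 | 0.727 |
| 80% vs 60% | delayed arm only | 0.670 | 0.778 |
| 60% vs 40% | immediate arm only | 0.593 | 0.711 |

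Reading 20% as a relative difference (65.5% vs 54.5%) gives 0.228 two-sided. Rates of 90% vs 70% would give 0.789 two-sided and 0.871 one-sided, but they imply 20% overall non-use and fit no reading of the stated 40%.

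**Unequal allocation.** For 70% vs 50%, two-sided, the best split of 120 is 62/58, still 0.611; 2:1 (80/40) gives 0.572 or less.

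**Level that would give 0.80 with 60 per arm:** one-sided about 7.9% (70% vs 50%) or 5.8% (80% vs 60%). A one-sided 10% level gives 0.835 for 70% vs 50%.

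**If 120 were per arm:** power would be 0.890, but 150 enrolled women cannot supply 240.

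**Detectable difference with 60 per arm,** two-sided 5%, centred on 60% use, 80% power: about 25 points. Check at 72.5% vs 47.5%: (0.25 × √60 − 1.358) / √(0.1994 + 0.2494) = (1.936 − 1.358) / 0.670 = 0.864, and Φ(0.864) = 0.806 (exact 0.810).

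**The case against.** The strongest reply is that the plan gives no level, sidedness or arm rates, so 61% rests on assumptions and a calculation at another level cannot be ruled out. The primary hypothesis in section 2.1.1 is directional: "Women who receive Nexplanon immediately post abortion will be significantly more likely to be using the device 6 months after the procedure". At a one-sided 5% level with 80% vs 60%, power is 0.778, or about 0.79 with unpooled variance, a near miss. That part stands: the size of the shortfall depends on the reading. But the near miss requires a one-sided test that is nowhere specified, and it requires taking the 40% as the delayed arm's rate although the plan applies it to all women. Even then it does not reach 0.80. Nothing in the document points to a one-sided 10% level.

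A second reply is that more than 120 women might be analysed, since section 2.7 specifies intention-to-treat and does not say how unreached women are counted. With all 150 analysed (75 per arm), two-sided power is 0.709 for 70% vs 50%, 0.767 for 80% vs 60% and 0.691 for 60% vs 40%. One-sided 5% figures are 0.809, 0.854 and 0.794. Some one-sided readings thus pass 0.80 at 150, but section 2.7 ties the power to 120 and treats the other 30 as an allowance for losses.

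A third reply is that the real effect may be far larger. The earlier IUD trial cited in section 2.2 found 81.7% vs 28.4%, for which 60 per arm give power above 99.9%. The trial may well succeed on such an effect. It is not the stated planning difference, however, so it does not support the sentence. Nor does low power bias the comparison or inflate the type I error; the fault lies in the stated assurance.

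**Conclusion.** The concern holds. At a 5% level, 120 evaluable women do not give 0.80 power for a 20-point difference under any reading of the 40% non-use examined. On the literal reading (70% vs 50%), with two-sided 5% and 1:1 allocation assumed, power is about 61% and the risk of missing the difference is 1 − 0.611, about 39%. The evaluable number needed is 186 rather than 120. The conclusion concerns the stated planning difference only. The exact shortfall depends on inputs that the plan omits, and that omission is part of the fault because the claim cannot be verified as written.

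**What to change.** Amend the sample size paragraph of section 2.7:

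1. State the significance level and sidedness actually used, the allocation ratio (1:1 if intended) and both assumed arm rates.
2. For a two-sided 5% test at 1:1, replace the 0.80 claim with one of two statements: 120 evaluable women give about 61% power for 70% vs 50% use; or they give 80% power for a difference of about 25 points (72.5% vs 47.5%). Label the second as the detectable difference at the fixed sample size, not as the original planning target.
3. If the calculation was made at another level, report that level and the matching figures. Do not choose a level afterwards to fit 120.

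This changes wording only. Enrolment, endpoint and test stay as they are. The cost is a less favourable stated power or a larger stated detectable difference. Keeping the 0.80 claim for 70% vs 50% at two-sided 5% would instead mean 186 evaluable women, about 233 enrolled at the plan's own 20% loss.

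### Nothing in the plan keeps the 6-month caller unaware of arm or insertion status, and call attempts have a minimum but no common schedule, so reach could depend on use differently by arm

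*Combined protocol and SAP*

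**What the plan says.** **Who calls.** Section 2.5 (Interventions): "All participants will receive a phone call from a research assistant at 6 months to complete a Satisfaction Questionnaire". The same section has the woman feel for her implant during that call, within 2 weeks either side of 6 months, and adds: "Phone calls completed out of window will be documented as a protocol deviation".

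**How hard they try.** Section 2.7 (Withdrawals, Losses and Deviations): "Research staff will make at least three attempts to contact participants by phone at 6 months". Then: "If these attempts are unsuccessful a certified letter and U.S. mail letter will be sent", and the emergency contact is approached if the certified letter comes back unopened. All of this is worded identically for both arms.

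**How the answer is scored.** Section 2.7: "If the device is palpable she will be considered as using Nexplanon at 6 months". A woman who cannot feel the device is brought to the clinic for evaluation by a clinician.

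**Who is masked.** Section 2.7 (Blinding): "After randomization, neither the participants nor the physicians will be blinded to the treatment". Research staff are not mentioned.

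**What else research staff do.** Under section 2.5 they send the delayed arm one appointment reminder, and a woman who misses that visit arranges any later insertion with the research office. A staff-administered questionnaire is completed at the delayed insertion visit.

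**The concern.** Participants and the operator cannot be masked in this design. The person who telephones at 6 months largely can be, and the plan does not provide for it.

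This matters because of what the study file can show. Section 2.5 states that the clinic offers the device only through the study and that one physician places every study implant. A delayed-arm woman with no insertion on record is therefore a likely non-user before anyone dials. In the immediate arm the implant goes in before the woman leaves, so the insertion record does not predict non-use. A caller who can see arm and insertion status has information about the likely answer in one arm only, and the plan does not say when attempts beyond the third are made, or for whom.

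The primary analysis is a chi-square comparison of two percentages, in a population that the plan itself considers likely to be lost. If the chance of being reached depends on use differently in the two arms, the women who answer no longer give a fair comparison.

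**Working it through.** **Plan figures used.** Section 2.7 enrols 150 to end with 120, an implied loss of 1 − 120/150 = 20%; conversely 120/(1 − 0.20) = 150, so that step reproduces. It plans for a 20-point difference with 40% overall not using. With equal arms (1:1 is assumed, as the ratio is not stated) this is 70% against 50%. The plan's 120 is not reproduced at those rates (two-sided 5%, 80% power needs 93 per arm, 186 in all). That is a separate matter and nothing below depends on it.

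**Model.** Let p be true use in an arm, u the proportion of users reached and n the proportion of non-users reached. Then

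observed use among women reached = p·u / (p·u + (1 − p)·n).

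Every u and n below is an assumption; the documents give none.

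**Step 1: when does unequal reach create a false difference?** True use is set at 60% in both arms, with 75 women per arm.

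| Immediate u / n | Delayed u / n | Observed use | False gap | Chance of p<0.05 |
|---|---|---|---|---|
| 90% / 90% | 70% / 70% | 60.0% vs 60.0% | 0 | 5% |
| 90% / 65% | 90% / 65% | 67.5% vs 67.5% | 0 | 5% |
| 90% / 70% | 80% / 80% | 0.54/0.82 = 65.9% vs 60.0% | 5.9 points | about 10% |
| 90% / 65% | 75% / 85% | 0.54/0.80 = 67.5% vs 0.45/0.79 = 57.0% | 10.5 points | about 22% |

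The last column is a normal approximation, two-sided. Row 1 shows that more effort in one arm, unrelated to use, does not bias the comparison among women reached. Row 2 shows that reach depending on use equally in both arms creates no false gap (with true use of 70% and 50% it would shrink 20 points to 76.4% − 58.1% = 18.3). Rows 3 and 4 show that a false gap appears when the dependence differs by arm. In row 4 overall reach is almost equal, 80% against 79%.

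Row 1 changes if women never reached are counted as non-users: 0.60 × 0.90 = 54% against 0.60 × 0.70 = 42%, a false gap of 12 points. The plan has no rule on this.

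**Step 2: which way could it go?** Take true use of 70% and 50%, with the immediate arm reached at 80% regardless of use, so that it shows 70%.

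- Staff stop early for delayed-arm women with no insertion: u = 90%, n = 70%. Observed delayed use is 0.45/(0.45 + 0.35) = 56.25%, and the gap is 13.75 points.
- Staff press harder for those same women: u = 70%, n = 90%. Observed delayed use is 0.35/(0.35 + 0.45) = 43.75%, and the gap is 26.25 points.

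Overall delayed-arm reach is 80% in both cases. The same knowledge can shrink or widen the gap by 6.25 points.

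**Step 3: scoring.** For the caller to distort scoring, the palpation step must be skipped. If a bare yes were accepted from 5% of immediate-arm non-users (30% of that arm), the effect would be 0.30 × 0.05 = 1.5 points, and it would require a departure from the written procedure.

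**Step 4: what masking would not reach.** Contact details are reviewed at the delayed insertion visit. Only delayed-arm women who attend get that update, and they are the likely users of that arm. This could make reach depend on use whoever makes the call.

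**The case against.** The best defence has four parts.

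1. **The plan does not say that the caller knows the arm.** This stands. A reader might infer that the callers are unmasked as a matter of record. The blinding statement covers only participants and physicians, and the reminder is assigned to research staff while the call is assigned to a research assistant; no section says they are the same person. Knowledge of arm is a reasonable inference from silence and from the tasks handled by the research office, but it is an inference.

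2. **The contact procedure is the same for both arms and does not end at three calls.** This also stands. Letters, the emergency contact, two outside contacts taken at enrolment, a call window and a \$25 card on completion all apply to both arms. An identical written minimum still allows actual effort to differ without any deviation being recorded.

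3. **Scoring leaves little discretion.** Largely correct. A palpable device counts as use, and a clinician checks when it cannot be felt. A false report by a woman who knows her own allocation would not be cured by masking the caller.

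4. **The shifts are assumed and modest.** With 60 per arm at 70% and 50%, the 95% half-width is 1.96 × √(0.21/60 + 0.25/60) = 17 points. Bias does not average out as random error does, but this supports treating the point as a cheap improvement rather than a serious defect.

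A reader might also want to cap the number of attempts. That does not follow. Suppose 60 of 75 delayed-arm women are reached with 50% use, and the other 15 have 25% use. The true figure is (30 + 3.75)/75 = 45.0%. Reaching seven more gives (30 + 1.75)/67 = 47.4%, closer to the truth than 50.0%. A cap could increase missing outcomes in a population already expected to be hard to trace.

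**Conclusion.** The point holds in a limited form. The plan does not keep the 6-month caller unaware of arm or insertion status, gives no common attempt schedule, and has a study record that can identify likely non-users in one arm only. Reach could therefore depend on use differently by arm, with about 20% of outcomes expected to be missing.

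Under the assumed reach rates, false gaps are 5.9 to 10.5 points where true use is equal, and a true 20-point gap becomes 13.75 or 26.25. These show what would be needed; they are not estimates of what will happen.

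A reader might infer that the arrangement favours immediate insertion. The documents do not support a direction: stopping early on delayed-arm women without an insertion shrinks the gap, and pursuing them harder widens it. Nor do they support the inference that unequal effort alone biases the comparison among women reached, or that the caller has wide latitude in scoring.

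**What to change.** - Give the 6-month caller a list with name, contact channel and due date only, without arm or insertion date. Where possible, assign each call to existing staff who did not handle that woman's reminder or insertion visit.
- Record the use-and-palpate item before any item that reveals arm.
- Keep the minimum of three attempts and the existing letter and emergency-contact steps. Apply the same attempt schedule to every woman and log each attempt.
- Report attempts and reach by arm. This also helps show whether the contact-detail update at the delayed visit has affected reach, although row 4 of the table shows that similar overall reach does not rule out bias.

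**Cost.** A filtered list, a reordered script, a short protocol change and a little extra work for logging. Masking will be partial where staff remember a participant or she mentions her allocation. The change does not settle how women never reached are scored, which needs its own rule.
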